Due to the high cost of sugammadex, some researchers have hypothesized that a lower dose is required when combined with neostigmine. A 2015 study from Beirut in adults undergoing elective surgery demonstrated that a dose of 2 mg/kg of sugammadex combined with neostigmine 0.05 mg/kg was non-inferior to the standard dose of 4 mg/kg of sugammadex in reversing deep NMB, defined as returning from a TOF count of 0 to a TOF ratio of 0.9 within 5 minutes, with similar times to extubation as well as no cases of recurarization in the post anesthetic care unit (PACU) (16). Lobaz, Sammut and Damodaran reported in 2013 the use of sugammadex as rescue therapy for a 71-year-old patient with end stage renal disease who was unable to be weaned off the ventilator almost five hours after receiving a single 1.2 mg/kg dose of rocuronium. He had initially achieved a TOF of 4, was reversed with 2.5 mg of neostigmine 45 minutes after induction, but failed to maintain adequate spontaneous ventilation despite his TOF remaining at 4, and was transferred to the intensive care unit 3 hours post induction. There, his TOF steadily declined to 2, as a result of which he received a 6 mg/kg dose of sugammadex, causing him to be successfully extubated ten minutes later (17). It is similarly important to dose sugammadex appropriately; Carollo et al. published a case report in 2019 of an 8-month-old patient who had recurarization after a 4 mg/kg dose of sugammadex was given with a TOF count of 2/4, which fortunately resolved after a second 4 mg/kg dose of sugammadex (18).

Lastly, known common adverse effects of neostigmine include bradycardia, nausea and vomiting (19), while the use of sugammadex has been found to lead to nausea, vomiting, hypotension and headache in \geq 10% of patients (5). There have also been case reports of marked bradycardia possibly leading to cardiac arrest with the use of both agents.

Page 6 of 30 Version: 3 (10/14/2024)

4. Study Endpoints

Primary study outcome:

The time taken to achieve a TOF ratio of 0.9 after the use of the intervention drug versus placebo in a patient population that has already received neostigmine for NMB reversal.

Secondary study outcome:

The percentage of patients who achieve a TOF ratio of 0.9 within 1 minute, 2 minutes, 5 minutes, and 10 minutes.

Safety outcomes:

The incidence in PACU (measured in %) of:

- i. Nausea,
- ii. Vomiting,
- iii. Bradycardia²,
- iv. Tachycardia³, and
- v. Hypotension⁴.

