For the safety outcomes, patients who were recruited but did not receive the intervention drug will be compared to patients who did receive the intervention drug to determine if their rates of adverse effects are similar. However, the sample size in this study is too low to perform formal non-inferiority tests on this data.

5. Study Intervention/Investigational Agent

Study intervention:

Patients will be randomized to six groups: 2 mg/kg (the lowest dose approved by the FDA), 1 mg/kg, 0.5 mg/kg, 0.25 mg/kg, 0.125 mg/kg of sugammadex and placebo (normal saline).

The Grady Memorial Hospital operating room pharmacy will store and dispense the study drug, while the anesthesia provider in the operating room will administer it.

As elaborated before, sugammadex is a FDA-approved drug that is in routine clinical use for NMB reversal.

Page 7 of 30 Version: 3 (10/14/2024)

² Heart rate < 60 beats per minute over two or more recordings if not present pre-operatively

³ Heart rate > 100 beats per minute over two or more recordings if not present pre-operatively

⁴ Systolic blood pressure < 90 mmHg and/or mean arterial pressure < 65 mmHg over two or more recordings

The study protocol was submitted to the U.S. FDA, and found to be exempt from IND regulations (PIND 162798 dated 2022-Jul-13).

6. Procedures Involved

This project is a double-blind randomized placebo-controlled dose-response trial that aims to determine the time taken to achieve adequate reversal comparing five doses of sugammadex as rescue therapy following inadequate reversal with neostigmine.

We will identify patients in the Grady Memorial Hospital OR who are scheduled to undergo an elective surgery under general anesthesia, received rocuronium for NMB and neostigmine for NMB reversal, and achieved a TOF count of at least 3 twitches but not a TOF ratio of 0.9 fifteen minutes after neostigmine has been given.

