- Did not require general anesthesia for surgery,
- Did not require NMB,
- Did not receive neostigmine for NMB reversal,
- Had a TOF count < 3 or a TOF ratio ≥ 0.9 fifteen minutes after neostigmine, or
- Remained intubated in the immediate postoperative period.

As the study intervention is a one-time dose of the study drug in the OR, no further action should be required if the patient decides to later withdraw from the study. The study will be terminated when the number of participants has reached the required threshold.

17. Risk to Participants

The most common risks of sugammadex as listed by the FDA (5) include:

- Nausea (23-26%)
- Vomiting (11-15%)
- Pain (36-52%)

Uncommon but serious risks of sugammadex include:

- Hypotension (4-13%)
- Tachycardia (2-5%)

Page 12 of 30 Version: 3 (10/14/2024)

- Bradycardia (1-5%)
- Anaphylaxis (0.3%)

Notably, all of these are known to be risks of general anesthesia as well as surgery and are routinely monitored for and treated in the PACU.

18. Potential Benefits to Participants

All study subjects will have any residual NMB reversed, which will prevent any postoperative complications such as respiratory compromise or weakness.

19. Compensation to Participants

N/A

20. Data Management and Confidentiality

Data to be collected include:

- Baseline demographics: MRN, date of birth, sex (male/female), race (white, black, American Indian or Alaska Native, Asian, Native Hawaiian or Other Pacific Islander, two or more races), ethnicity (Hispanic or Latino, not Hispanic or Latino), weight (kg)
- ii. Preoperative details: ASA status (I-IV)
- iii. Surgery details: date of surgery, diagnosis, surgery, start case time (hr: min), end case time (hr: min)
- iv. Anesthesia details: if succinylcholine was used (Y/N), total amount of rocuronium given (mg), the last dose of rocuronium that was given (mg), the time that the last dose of rocuronium was given (hr:min), neostigmine dose (mg), the time that neostigmine was given (hr: min), the time that the study drug was given (hr: min).
- v. TOF ratio (0-1)
 - Before any paralytic is given at the start of the case
 - Before neostigmine is given at the end of the case
 - Before the study drug is given
 - 30 minutes after PACU arrival
- vi. TOF count (0-4 ± fade)
 - Before neostigmine is given at the end of the case
 - Before the study drug is given
- vii. The time taken to achieve a TOF ratio of 0.9 (seconds).

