- viii. Postoperative details: if there was any of the following adverse effects: nausea, vomiting, bradycardia, tachycardia, hypotension (Y/N).

Page 13 of 30 Version: 3 (10/14/2024)

Baseline demographics and postoperative complications will be collected for patients who were enrolled but did not meet the study inclusion criteria to receive the intervention drug and their data will be used as a control group for the safety outcomes.

The data collection form is in the Emory University REDCap database but a similar form has been attached to this protocol as an Excel spreadsheet. Data would be collected by the study team in the OR and PACU. Data will be stored on the Emory University REDCap and OneDrive databases and may also be sent confidentially between study team members through the Emory University Outlook email network. The REDCap and OneDrive databases as well as the Outlook email network are all secure, encrypted and password protected. Paper consent forms will be stored in a locked box in the principal investigator's office at Grady Memorial Hospital. All data and records will be retained for at least 6 years following study completion.

Results will be reported in an aggregate form and in a de-identified manner. The form with protected health information (date of birth, date of surgery and MRN) will be recorded on a form separate to the form with data to be analyzed. Only study team members will have access to the form that links the study IDs with protected health information. [name], the biostatistician for the Emory University Department of Anesthesiology, will conduct the data analysis in collaboration with the principal investigator.

If a participant declines to participate in all portions of the study, the participant will not be assigned a study ID number and the study team members will refrain from collecting any data on the participant. If the participant agrees to participate in some portions of the study but not others, the participant will be assigned a study ID number and the study team members will be instructed to collect data only on those aspects of the study to which the participant has agreed to participate. These procedures will help prevent unauthorized inclusion of the patient's data in the database.

21. Plans to Monitor the Data to Ensure Safety of Participants and Data Integrity

X More than minimal risk

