Review our Data and Safety Monitoring Questionnaire and insert the relevant monitoring table at the end of this section. Also upload the completed questionnaire in the "Basic Study Information" smartform section in eIRB, question #8, as a separate document.

| S | Select one of the following: | | |
|---|------------------------------|--|--|
| | ☐ Medium Complexity | | |
| | ☐ High Complexity Category A | | |

The study team will review the safety endpoints (nausea, vomiting, bradycardia, hypotension) on a monthly basis for the duration of the study. These safety endpoints are collected at each study visit and recorded in the study database. Patients are routinely assessed for these side effects in the PACU by their bedside nurse as well as the anesthesia resident who is responsible for discharging them from the PACU.

| | | Subgroup n=6 | | Total N=36 | |
|-------------|---|--------------|---------------------|------------|---------------------|
| Event | Assumed Probability Risk (upper end) | p<0.01 | Safety cut short if | p<0.01 | Safety cut short if |
| Nausea | | | | | |
| (high) | 0.25 | p=0.0046 | n≥5 | p=0.0086 | n≥16 |
| Vomiting | | | | | |
| (high) | 0.15 | p=0.0059 | n≥4 | p=0.0048 | n≥12 |
| Bradycardia | | | | | |
| (high) | 0.05 | p=0.0022 | n≥3 | p=0.0083 | n≥6 |
| Hypotension | | | | | |
| (high) | 0.15 | p=0.0059 | n≥4 | p=0.0048 | n≥12 |

Using the binomial equation (see below), we calculated the probability of seeing a set number of patients in each group, if the actual probability in the normal surgical population is at the level specified in the 'assumed probability' column.

For example, if the 'normal' probability of nausea is up to 25% (that is, the risk with treatment is the same as the risk under standard surgical conditions), then the chance of having 5 or more patients with nausea in any one treatment group is 0.0046, and the chance of having 16 or more patients with nausea in total is p=0.0048. Since this is unlikely, we will reject the null hypothesis, and conclude that the actual risk in our trial is actually higher than that. So if 5 or more patients report nausea in any one group or if 16 or more patients report nausea in total, this would trigger a suspension of the trial for further review.

Page 15 of 30 Version: 3 (10/14/2024)

$$P(X \ge x) = \sum_{x}^{N} {N \choose x} p^{x} (1-p)^{(N-x)}$$

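### The two-recording rule for bradycardia, tachycardia and hypotension has no clause for treated episodes, so one corrected before a second abnormal recording is scored as no event

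*Combined protocol and SAP*

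**What the plan says.** Section 4 lists bradycardia, tachycardia and hypotension in the PACU among the safety outcomes, and three footnotes define them:

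- Bradycardia: "Heart rate < 60 beats per minute over two or more recordings", provided it was absent before the operation.
- Tachycardia: "Heart rate > 100 beats per minute over two or more recordings if not present pre-operatively".
- Hypotension: "Systolic blood pressure < 90 mmHg and/or mean arterial pressure < 65 mmHg over two or more recordings".

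None of the footnotes says how to score an episode that was treated. None says whether the recordings must be consecutive or how far apart they are taken.

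Section 17, after listing the risks of sugammadex (these three included), says that they "are routinely monitored for and treated in the PACU". Section 20, item viii, records each event as a yes/no answer, with no field for treatment or for a single abnormal reading.

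Section 21 states: "The study team will review the safety endpoints (nausea, vomiting, bradycardia, hypotension) on a monthly basis for the duration of the study". Its table sets suspension counts for those four events, per dose group of 6 and for all 36 patients. Tachycardia has no row. Section 21 neither repeats nor cites the footnotes, and it offers no other definition. It separately collects serious and other adverse events up to PACU discharge.

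**The concern.** A rule that needs two abnormal recordings treats a promptly corrected episode as if nothing had happened. Two untreated readings of 58 beats per minute make a bradycardia event. One much lower reading that staff treat at once, with success, does not. In that situation the rule drops an episode that staff judged to need treatment and keeps a milder one that they did not.

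This matters here because the Background says: "There have also been case reports of marked bradycardia possibly leading to cardiac arrest with the use of both agents". Every randomised patient has already had neostigmine. Cardiac arrest is collected separately under Section 21. What the endpoint can lose is the treated bradycardia that stops short of arrest.

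Two outputs are exposed: the reported percentages for the three events, and the fixed suspension counts for bradycardia and hypotension. Missed episodes can only lower a count, never raise it.

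**Working it through.** **1. The plan's own figures.** Section 21 uses the upper binomial tail, P(X ≥ r) with X ~ Binomial(n, p). Its bradycardia and hypotension figures reproduce to four decimals:

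| Event | Assumed risk | Group of 6 | All 36 |
|---|---|---|---|
| Bradycardia | 0.05 | P(X ≥ 3) = 0.0022 | P(X ≥ 6) = 0.0083 |
| Hypotension | 0.15 | P(X ≥ 4) = 0.0059 | P(X ≥ 12) = 0.0048 |

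**2. Effect of missed episodes.** Let p1 be the true risk of any abnormal episode, and q the share of event patients whose episode is corrected with no second abnormal recording. The counted risk is p1 × (1 − q), so the reported incidence is understated by the factor 1 − q.

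Neither p1 nor q is in the documents. The values below are assumptions: p1 = 0.15 for bradycardia (three times the plan's 0.05), p1 = 0.30 for hypotension (twice the plan's 0.15), and q from 0 to 50%. Patients are taken as independent with one common risk.

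| q | Bradycardia: counted risk | Chance of ≥ 6 of 36 | Hypotension: counted risk | Chance of ≥ 12 of 36 |
|---|---|---|---|---|
| 0 | 0.150 | 46% | 0.300 | 39% |
| 10% | 0.135 | 36% | 0.270 | 25% |
| 25% | 0.1125 | 21% | 0.225 | 9% |
| 50% | 0.075 | 5% | 0.150 | 0.5% |

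For hypotension at q = 50%, the counted risk is 0.30 × 0.5 = 0.15. That is the plan's own assumed risk, so a doubled true risk would look normal.

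**3. Effect of counting treated single readings while the cut-offs stay as printed.** Suppose the plan's 5% and 15% describe repeated-reading events. The ordinary risk under the wider definition is then p0 / (1 − q), and the chance of a review when nothing is wrong rises:

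| q | Bradycardia: ordinary risk | Chance of ≥ 6 of 36 | Hypotension: ordinary risk | Chance of ≥ 12 of 36 |
|---|---|---|---|---|
| 0 | 0.050 | 0.0083 | 0.150 | 0.0048 |
| 25% | 0.05 / 0.75 = 0.067 | 0.030 | 0.15 / 0.75 = 0.200 | 0.042 |
| 50% | 0.05 / 0.5 = 0.100 | 0.145 | 0.15 / 0.5 = 0.300 | 0.391 |

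If the 5% and 15% already describe any abnormal episode, this inflation does not arise. Section 17 cites ranges of 1-5% for bradycardia and 4-13% for hypotension without saying how those events were defined, so the documents do not settle which case applies.

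**The case against.** Requiring a repeat reading is a reasonable, pre-specified guard against artefact. That stands; the gap is the missing treatment clause, not the repeat reading.

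The mechanism has limits. No section says that treatment follows the first reading, how often values are recorded, or how often treatment works before the next one. The footnotes do not require consecutive readings, so a second abnormal value at any time in the PACU still counts. A reader might infer that every treated episode is lost, or that the rule systematically discards the most severe ones. The documents support neither: only episodes with no second abnormal recording are lost.

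A reader might also infer that all three events have weakened suspension counts. Tachycardia has none. For the other two, the link from Section 21 to the footnotes rests on the shared term for safety endpoints and on the absence of any other definition. That makes it the natural reading, not a stated one. Because the definition behind the assumed 5% and 15% is not given, the plan's cut-offs cannot be shown to be miscalibrated in one direction.

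Much of the low chance of triggering comes from the small sample and strict cut-offs. With no episodes missed, the rule would trigger only 46% and 39% of the time at the assumed risks.

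Oversight is not blind to a treated episode. Section 21 collects other adverse events, and its monitoring table has the principal investigator review data as collected and all adverse events monthly. That is a real mitigation, but nothing carries those reports into the endpoint percentages or the suspension counts.

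Finally, the comparison of dosed with undosed recruits uses one definition for both groups, so it is less clearly affected than the absolute rates. Treatment-based scoring brings its own risk: the undosed group is not blinded, so decisions to treat could differ between groups.

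**Conclusion.** The point holds as a gap in the scoring rule. Under the footnotes as written, an episode treated and corrected before any second abnormal recording is scored as no event. This can understate the three reported rates and, if Section 21 uses the endpoint definitions, the bradycardia and hypotension suspension counts.

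For a given patient, the direction of the scoring error follows from the wording. Its frequency cannot be found from the documents. The tabulated losses are illustrations resting on assumed true risks and an assumed q: about 10 percentage points for bradycardia and 14 for hypotension at q = 10%, and about 25 and 30 points at q = 25%. They are not estimates for this trial. The change is worth making because it is cheap and keeps the artefact guard, not because a large bias has been shown.

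**What to change.** 1. Amend footnotes 2 to 4 so that an event is two or more recordings beyond the limit, or any single recording beyond the limit for which treatment was given, as documented in the PACU record. Keep the existing pre-operative exclusion in footnotes 2 and 3.
2. Add a treated (Y/N) field beside each of the three events in Section 20, item viii.
3. State in Section 21 that the bradycardia and hypotension counts use this definition, and say which definition the assumed 5% and 15% refer to.
4. Report the rates under both definitions, for dosed and undosed patients, so that differences in ascertainment can be seen.

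This concerns scoring only and does not touch how patients are treated.

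The cost is three footnotes, one yes/no field per event taken from the PACU record, and two sentences in Section 21. The downside is that more events are counted against unchanged cut-offs. If the assumed risks describe repeated-reading events, a review would be triggered more often than the stated p<0.01: at q = 25%, 0.030 instead of 0.0083 for bradycardia and 0.042 instead of 0.0048 for hypotension, and more if q is larger. The clarification in item 3 is what lets the team judge whether that applies.

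### The bradycardia and tachycardia definitions have no criterion for worsening, so a patient already past the limit before surgery can never score that event; for bradycardia this also lowers the suspension counts

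*Combined protocol and SAP*

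**What the plan says.** Section 4 lists five safety outcomes, introduced as "The incidence in PACU (measured in %) of". The three haemodynamic ones are defined in footnotes:

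- Bradycardia (footnote 2): "Heart rate < 60 beats per minute over two or more recordings if not present pre-operatively".
- Tachycardia (footnote 3): "Heart rate > 100 beats per minute over two or more recordings if not present pre-operatively".
- Hypotension (footnote 4): "Systolic blood pressure < 90 mmHg and/or mean arterial pressure < 65 mmHg over two or more recordings". It has no pre-operative proviso.

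The denominator of the percentage is not stated. The planned safety comparison is that "patients who were recruited but did not receive the intervention drug will be compared to patients who did receive the intervention drug".

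Section 21 adds a monitoring rule: "The study team will review the safety endpoints (nausea, vomiting, bradycardia, hypotension) on a monthly basis for the duration of the study". Its table sets cut-offs for a subgroup of 6 and for the total of 36. For bradycardia, with an assumed probability of 0.05, the cut-offs are 3 or more of 6 (p=0.0022) and 6 or more of 36 (p=0.0083). Tachycardia appears neither in that table nor in the monthly list.

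Section 20 records each of these events as yes or no. Its only listed pre-operative detail is ASA status; pre-operative heart rate is not among the data items.

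**The concern.** The proviso in footnotes 2 and 3 removes more than unchanged baseline findings. It also removes every further movement in the same direction. Applied as written:

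- Before surgery 62, PACU 58 and 57: bradycardia, yes.
- Before surgery 58, PACU 38 and 36: bradycardia, no.
- Before surgery 104, PACU 150 and 148: tachycardia, no.

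The small change scores and the large ones do not. The background section itself warns: "There have also been case reports of marked bradycardia possibly leading to cardiac arrest with the use of both agents". Every randomized patient has already received neostigmine, and no exclusion criterion in section 11 removes patients with a low resting rate.

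Two things are at stake. The reported incidence of both outcomes leaves out worsening in patients who started beyond the limit. For bradycardia, such patients also cannot contribute to a suspension count that was calibrated as if all 6, or all 36, could.

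**Working it through.** **Inputs.** From section 21: bradycardia reference probability 0.05, cut-offs 3 of 6 and 6 of 36, each set at p<0.01. Not in the documents, so assumed: the share q with a pre-operative rate below 60 (5% to 20%), and the true event rates of 15% and 20% used for illustration.

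**Step 1: reproduce the plan's figures.** The upper binomial tail is P(X ≥ r) = Σ C(n,x) pˣ (1−p)ⁿ⁻ˣ, summed from x = r to n.

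- n=6, r=3, p=0.05: 0.0022.
- n=36, r=6, p=0.05: 0.0083.

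Both match the table. One event fewer would give 0.0328 and 0.0324, so these are the smallest counts below 0.01. The arithmetic of the table is sound; the question is which patients can contribute to X.

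**Step 2: effect of patients who cannot score.** Suppose a share q cannot score and the event risk p is the same in both subsets. The rate that can be counted is then p(1−q), while the denominators stay at 6 and 36. For example, p=15% and q=20% give 0.15 × 0.80 = 12%.

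| Assumed q | P(≥6 of 36), true 15% | P(≥6 of 36), true 20% | P(≥3 of 6), true 15% |
|---|---|---|---|
| 0 | 0.46 | 0.75 | 0.047 |
| 5% | 0.41 | 0.70 | 0.041 |
| 10% | 0.36 | 0.65 | 0.036 |
| 15% | 0.31 | 0.59 | 0.031 |
| 20% | 0.26 | 0.53 | 0.026 |

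At the reference rate of 5%, the chance of reaching 6 of 36 falls from 0.0083 to 0.0051 at q=10% and 0.0028 at q=20%.

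**Step 3: is the denominator the main problem?** Recomputing the cut-offs on at-risk patients only (p<0.01, reference 0.05) leaves the total cut-off at 6 for any 27 to 36 at risk, and the group cut-off at 3 for 4 to 6 at risk. Changing the denominator alone therefore hardly moves the rule. The loss comes from events that cannot be counted.

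**Step 4: tachycardia.** There is no suspension figure to recompute. Only the reported percentage is affected. Each footnote masks its own direction only: a patient below 60 before surgery can still score tachycardia, and the reverse.

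**The case against.** The strongest reply is that leaving out pre-existing findings is an ordinary treatment-emergent convention, and that the proviso is needed. That is right. If it were simply deleted and 10% to 20% of patients merely stayed at a low baseline rate, those patients alone would reach 6 of 36 with probability 0.15 to 0.75, with no drug effect at all. This argues for keeping the exclusion of unchanged findings. It does not argue for excluding worsening.

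A second reply is that a severe fall is still seen. Section 21 collects serious and other adverse events up to PACU discharge, with investigator review at each data collection and monthly review of adverse events. This stands as a safeguard for the individual patient. It does not put the event into the bradycardia outcome or the suspension count, and the yes/no field keeps no value from which worsening could be recovered.

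Third, the size is unproven. That also stands. At q=0 there is no effect. The illustrative rates are three and four times the table's 5%. The per-group rule has little power at 15% in any case, so its absolute loss is small (0.047 to 0.026 at q=20%). Patients with a low baseline may also have a different risk from the others.

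Three stronger readings are tempting, and the documents do not support them:

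- A reader might infer that the tachycardia footnote weakens the suspension rule. It cannot, because tachycardia has no count there.
- A reader might infer that comparisons between doses are distorted by chance imbalance in baseline heart rate. No between-dose safety comparison is planned. The stated one is treated against untreated patients, and the same footnotes apply to both sides.
- A reader might take it as given that masked patients stay in the denominator of the reported incidence. Only the suspension table fixes denominators; for the incidence, all patients is the natural reading but is not stated.

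**Conclusion.** The point holds as a defect of definition. Under footnotes 2 and 3, a patient already beyond a heart-rate limit cannot score that event however far the rate moves in the same direction. For bradycardia the section 21 counts inherit this; for tachycardia only the reported incidence does. Because the rule as written gives a wrong score for identifiable patients, this is more than a missing detail.

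The direction is downward and the size is unknown. If q is 5% to 20% and risk is equal in both subsets, the chance of reaching 6 of 36 falls by 0.05 to 0.20 at a true 15% rate, and by 0.05 to 0.23 at a true 20% rate. Both q and the true rates are assumptions. The change should be made because it is cheap and concerns patient safety, not because a large loss has been shown.

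**What to change.** 1. In footnotes 2 and 3, count an event that is new, or that has worsened from an abnormal pre-operative value on two or more recordings by a margin the investigators fix in advance. Unchanged baseline findings stay excluded.
2. Use the same bradycardia definition for the section 21 counts.
3. Add pre-operative heart rate to the section 20 data items. The existing footnotes already need it. Record enough of the PACU heart rates to apply the margin, since a yes/no entry alone would not allow the scoring to be checked.
4. State the denominator of the reported incidence, and report new-onset incidence among patients without the condition pre-operatively.

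The cost is a few lines of wording, one routine chart field plus the PACU values behind the yes/no entry, a margin to choose, and a slightly higher chance that the trial is suspended for review.
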